## 4.4 Pilot distribution in the VMMC model

Two models of distribution will be employed for VMMC services . At static VMMC centres, distribution will occur as for New Start Centres: clients will be given the choice of PDHTC or HIVST. In the other model, distribution of kits will be done by community mobilisers to potential VMMC clients at community level. With VMMC distribution our aims are:

- 1. To determine the uptake of self-testing among men who visit PSI-managed VMMC centres in urban areas
- 2. To determine the acceptability of distributing self-test kits to potential VMMC clients during community-based mobilisation for VMMC
- 3. To determine the cost and cost effectiveness of distributing self-test kits through PSI 's VMMC services

Detailed procedures are given in Appendix 2, Standard Operating Procedures (SOP) for the VMMC Model.

## 4.5 Costing of distribution of test kits in the PSI New Start and VMMC systems

The costing study will adopt the provider's perspective: detailed costing of all resources used in the provision of HIVST and linkage services will be done. Cost data will be collated from project accounts as well as time and motion studies. An ingredients based approach will be used to collect costs based on actual expenses for capital items, and recurrent costs. The costing procedures will be done according to written standard operating procedures.

## 4. 6 ENSURING DATA QUALITY

CeSHHAR Zimbabwe has considerable expertise in supporting all aspects of quality data management. Standard Operating Procedures (SOP) will be used on study design, data collection instruments and data analysis procedures, with routine data quality audits conducted for quality assurance purposes. CeSHHAR have also invested in electronic data collection, using open source software and computer tablets. This approach improves data collection efficiency and reduces traditional weaknesses associated with data collection such as completeness, consistency, and timeliness. CeSHHAR have an internal research monitoring committee who are tasked with ensuring data quality and adherence to GCP. In addition, LSHTM will work with the local team to support data quality.

## **5 ETHICAL CONSIDERATIONS**

Ethical approval of the research will be sought from the local institutional review board (IRB) in Zimbabwe, and the IRBs of relevant participating institutions: London School of Hygiene &Tropical Medicine and University College London. No research procedures will take place until approval from these ethical review boards has been granted. Procedures will be implemented in a way that upholds the confidentiality of client data. The trial will be conducted in accordance with GCP, and all staff will receive GCP training. The bulk of the data will be programmatic; and is anonymised. The database of client contact details will be kept separate from that which has client demographic and clinical information. Written informed consent for participation in the surveys, discrete choice experiments and qualitative studies will be obtained.

## Governance

The study may be subject to audit by the London School of Hygiene & Tropical Medicine under their remit as sponsor, the Study Coordination Centre and other regulatory bodies to ensure adherence to GCP.

STAR will form a Technical Advisory Group (TAG) to monitor and supervise progress of data collection, provide independent review of data collected during all CRTs conducted under the STAR project, and assist investigators in disseminating results.

## Adverse Event Reporting and Management

HIV testing and counselling, including HIVST, is well established, and known to have a high level of safety and favourable risk: benefit ratio. However, harmful reactions can occur. For the purposes of this trial, we will focus on capture of the following Serious Adverse Events (SAE). This includes:

- Death or hospitalisation due to self-inflicted injuries within 30 days of a positive HIVST results
- Death or hospitalisation resulting from violent assault by others (intimate partner violence, assault by family members, assault by community members) within 30 days of a positive HIVST result

Ongoing surveillance for social harms and adverse events will be done according to methods described in section 4.1.5.

In addition, CDBAs will also be trained in how to identify, categorise and refer SAEs. The CBDAs will determine if the incident is related to the study. Serious and study-related incidents will be reported immediately to the study leadership. The study leadership will then report directly to relevant authorities including the ethics committees. Non-serious but study-related incidents will be documented and reported at the end of the month. They will be reviewed by a designated employee. If it is deemed that a particular incident was misclassified, the CBDAs and their supervisors will be asked to review/ investigate the incident again and use appropriate documentation for serious incidents related to the study.

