## 4.2.3 Distribution of self-test kits and PSI programme activities

HIV self-test kits will be distributed by CBDs to all households in the study communities. CBDs will ensure that each household receives a kit for each member of the household who is willing to test. At time of kit distribution, CBDs will give out appointment cards on which clients will document the intended date and time of performing the self-test. This will ensure that clients make a commitment to self-test (an intervention that previous research has proven effective in ensuring future uptake of health interventions [23, 24]). CBDs will inform clients of the date of the next PSI outreach visit, and encourage them to think about the time that they would like to attend the outreach clinic. The client will be asked to write this time on their card, which will help foster a commitment to attend post-test services. The card will have the CBD identity number, and clients will be asked to take it to the outreach clinic.

Once they have self-tested, clients/participants will be asked to complete a short results form and to return both the form and the used test kit in a sealed envelope to a drop-off point in the community. The used kits will be placed in locked boxes that will be kept at health facilities. In addition, CBDs will also keep locked drop-boxes where clients can deposit their used test kits. No client identifiers will be placed on the used test kits, although it will be possible to know which household the kit came from. On a weekly basis PSI will collect the sealed boxes. Only authorised PSI staff will have the keys to the drop boxes. A late read of results of the returned kits will be done to estimate HIV prevalence among the HIV self-testers.

One to two weeks after self-test kits have been distributed to households within a community, a PSI outreach team will visit the community to provide a comprehensive package of services packaged as 'well woman' and 'well man' services. These services will include client-initiated counselling and

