## 4.2.4 Description of study interventions

## Incentives for CBDs

During training, CBDs in communities that have been randomised to CBD incentives for linking selftesters to post-test services will be told that they will get a stipulated amount of money (20c) for each self-tester who attends the PSI outreach site after testing. Upon attendance at outreach sites, all clients who report having self-tested will be asked to show their self-completed appointment card (which bears the CBD identity number) to PSI staff. Staff will keep a log of clients that attend according to CBD in order to facilitate payment of the CBD. If a client has not brought their appointment card, they will be asked to provide the name of the CBD who supplied the self-test kit, which will be verified with CBD kit distribution records in that area before the CBD is credited with the attendance.

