## Institutional responsibilities

SAEs will be reported immediately to CeSHHAR. All other adverse events will be logged and reported through regular follow-up reports.

As this is a public-health scale-up evaluation, following an intervention trial in Malawi that showed low risk of harm from HIVST (no suicides from 27,000 HIVST episodes), expected SAEs will be reported through 6-monthly progress reports that will report on safety as well as other important process indicators and will be sent to the Technical Advisory Group (TAG) members and local and international collaborators.

12 monthly reports with full listings of SAEs will be submitted to Ethics Review Boards at the time of annual reporting.

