## **Reporting procedures**

SAE forms will be completed by the CeSHHAR project coordinator and responsible PSI Program Manager. The PI will check the form and make changes as necessary.

SAEs will be evaluated for seriousness and likely relatedness to HIVST by the Zimbabwean principal investigator.

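### Three safety-reporting sections disagree on whether the kit distributor's view of relatedness decides if a serious incident is escalated, and the SAE list covers only events after a positive self-test

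*Protocol*

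**What the plan says.** Three adjoining parts of the Ethical Considerations chapter set the rules.

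- **Adverse Event Reporting and Management** limits the SAEs of interest to death or hospitalisation from self-injury or from violent assault. Each is tied to a positive self-test; the assault item ends "assault by community members) within 30 days of a positive HIVST result". The section then adds a route through the CBDAs: "The CBDAs will determine if the incident is related to the study. Serious and study-related incidents will be reported immediately to the study leadership". Incidents that are not serious but are study-related are reported monthly, and a designated employee reviews them for misclassification.
- **Institutional responsibilities** has no relatedness condition: "SAEs will be reported immediately to CeSHHAR". Other adverse events are logged and go into regular follow-up reports.
- **Reporting procedures** gives the judgement to someone else: "SAEs will be evaluated for seriousness and likely relatedness to HIVST by the Zimbabwean principal investigator".

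Three other places bear on this. Section 4.2.4 (Incentives for CBDs) promises distributors in the incentive arm "a stipulated amount of money (20c) for each self-tester who attends the PSI outreach site after testing". Section 4.2.3 asks self-testers to "return both the form and the used test kit in a sealed envelope to a drop-off point in the community". Section 4.1.2 describes a toll-free line whose staff document social harms, and monthly contact with organisations that handle gender-based violence (GBV). The adverse-event section points to these surveillance methods as section 4.1.5, which does not exist.

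**The concern.** Whoever judges relatedness first decides what everyone downstream can see. If a lay distributor's judgement is a condition for escalation, the investigator's later assessment works only on events that passed that filter. In one arm the person applying the filter knows the allocation, has a small financial interest in attendance, and may be judging an incident connected with their own conduct. That is reason enough not to let this judgement gate escalation, whatever its effect in practice.

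The SAE list is a second, separate limit. Section 1.3 asks for procedures that detect any social harm from self-testing and warns that such harm may be hard to detect. The secondary objectives include GBV incidence in the communities, regardless of test result. A list conditioned on a positive result leaves out serious harm that those passages set out to find. At stake are participant safety and the completeness of the trial's account of harms. The primary outcome and the power calculation are not affected.

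**Working it through.** No arithmetic applies: the protocol gives no SAE rate, expected count or reporting probability. The check is to follow four incidents through the three sections. In all four, a person is hospitalised after an assault.

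| Incident | Adverse Event Reporting and Management | Institutional responsibilities | Reporting procedures |
|---|---|---|---|
| A. After a positive self-test; distributor thinks it related | To the study leadership at once | To CeSHHAR at once | Investigator judges |
| B. Same event; distributor thinks it unrelated | No onward step stated | To CeSHHAR at once | Investigator judges |
| C. After refusal, a negative result or a partner's result; distributor thinks it related | Outside the SAE list, but goes up at once if serious is read in its ordinary sense | Not a listed SAE, so logged for periodic reports | Covers SAEs only |
| D. Same as C; distributor thinks it unrelated | No onward step stated | Logged, if anyone passes it on | Covers SAEs only |

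**Row A.** The sections agree in effect.

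**Row B.** They contradict each other. The misclassification review does not rescue the event: it follows the sentence on non-serious, study-related incidents and is not stated to cover serious incidents called unrelated. Whether the investigator sees the event depends on which section the field team follows.

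**Rows C and D.** The unfiltered rule in Institutional responsibilities does not help, because the SAEs it refers to are those just defined. The condition is also hard for a distributor to verify. Used kits come back in sealed envelopes without client identifiers, and only authorised PSI staff hold the keys to the boxes. A distributor who helped with the test, or was told the result, may know it; others will not.

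**Relatedness to what.** The adverse-event section asks about relatedness to the study; Reporting procedures asks about relatedness to HIV self-testing. Both arms receive kits, and what is randomised is the distributor incentive. Harm from incentive-driven pressure could be study-related without being obviously related to self-testing, and no section asks the investigator about it.

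**Channels that bypass the distributor (section 4.1.2).** The toll-free line depends on someone calling. The monthly consultations yield numbers of GBV reports and their causes. Neither requires a positive result, so both can pick up rows B to D, but neither is stated to feed the SAE process.

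**The case against.** The strongest reply is that the distributor route is introduced as an addition to ongoing surveillance, not as the only path. Institutional responsibilities already sends SAEs on without a filter, the investigator already has the final judgement, and events outside the list are logged. This stands in part. A reader might infer that a serious incident called unrelated has no route at all. The documents do not support that: only the adverse-event section, read alone, lacks one. The reply does not remove the conflict between the sections.

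A reader might also infer that harms will be under-reported more in the incentive arm. The documents do not show this. The 20c is tied to outreach attendance, not to incident reports, and closer contact with clients could raise detection instead. The protocol also describes no comparison of SAEs by arm for such bias to distort. The 3% forced testing cited in section 1.3 is not evidence of pressure by distributors: it comes from a study in Malawi, and the forcing was often by main partners.

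Finally, a reader might try to size the gap from the national HIV prevalence of 15% in the Background, or from the absence of suicides in 27,000 self-test episodes in Malawi. The first is not the reactive fraction among trial self-testers, and it counts people rather than risk. The second concerns one outcome in another study. Neither tells how many events would be missed here.

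**Conclusion.** The concern holds as a contradiction in the reporting rules together with a narrow SAE definition. The adverse-event section makes the distributor's view of relatedness a condition for immediate escalation; the two sections after it do not, and one assigns that judgement to the principal investigator. Serious assault or self-injury without a positive self-test in the preceding 30 days is outside the SAE list, and the channels that might catch it have no stated link to SAE reporting.

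The size cannot be given. Differential under-reporting between arms is possible, but its size and direction cannot be derived from the protocol.

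The conclusion rests on three readings: that CBDA means the community-based distributor; that SAE in the later sections means the events listed in the first; and that the designated employee's review applies to the incidents named in the sentence before it.

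**What to change.** 1. Reconcile the three sections so that every serious incident a distributor learns of is forwarded to CeSHHAR and the principal investigator, whatever the distributor thinks of its relatedness. Define CBDA.
2. Have the investigator alone judge relatedness, separately to self-testing and to the distributor incentive.
3. Record serious self-injury and assault that reach the study through any channel, including the toll-free line and the GBV consultations, whether or not a positive self-test is known. Note the result if known, and tabulate by arm. This needs the community to be recorded: allocation is to be balanced on district, so a district-level GBV count may not separate the arms.
4. Change the reference to section 4.1.5 to section 4.1.2.

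The cost is a wording amendment, brief distributor training, a community field on incident records, and some additional unrelated events for the investigator to review. This does not ask for active follow-up of everyone for 30 days from kit receipt. That would cover all households in 38 communities, with used kits that carry no client identifiers, and would be a much larger undertaking.

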## Institutional responsibilities

SAEs will be reported immediately to CeSHHAR. All other adverse events will be logged and reported through regular follow-up reports.

As this is a public-health scale-up evaluation, following an intervention trial in Malawi that showed low risk of harm from HIVST (no suicides from 27,000 HIVST episodes), expected SAEs will be reported through 6-monthly progress reports that will report on safety as well as other important process indicators and will be sent to the Technical Advisory Group (TAG) members and local and international collaborators.

12 monthly reports with full listings of SAEs will be submitted to Ethics Review Boards at the time of annual reporting.

## **Reporting procedures**

SAE forms will be completed by the CeSHHAR project coordinator and responsible PSI Program Manager. The PI will check the form and make changes as necessary.

SAEs will be evaluated for seriousness and likely relatedness to HIVST by the Zimbabwean principal investigator.

## 6 STATISTICAL CONSIDERATIONS Sample size calculations

## 1) Linkage to post-test services

For our household survey, we will sample 200 participants per cluster. With 19 communities per arm we have >90% power to detect at least a difference of 10% linkage to post-test services in the control arm versus 15% in the intervention communities, assuming a coefficient of variation (k) of 0.3.

Percent linking in intervention areas		Power (assuming 200 respondents per cluster)
15%	10%	92%
7.5%	5%	83%
20%	14%	87%

## Data analysis

#### Pilot household survey data

Household survey collected in the first six clusters where HIVST distribution occurred but the linkage intervention did not will be analysed separately as pilot data.

#### Cluster randomised trial

The main statistical analyses for the cluster randomised trial will include (i) descriptive analyses of community characteristics by arm; and ii) outcome evaluation of the primary and secondary outcomes. Analyses will be intention-to-treat. A random effect will be included to account for clustering at site level. For binary outcomes, a random effects logistic regression model will be used. Intervention arm will be included as a covariate, and the model will adjust for cluster-level HIV prevalence and other key characteristics.

#### Population-based survey

The data from the population-based survey will be analysed using random effects logistic regression models to assess association between individual-level and community-level factors associated with accepting and using self-test kits, adjusted for clustered survey design using a random effects term for cluster.

#### Analysis of health facility data

To evaluate the effect of CBD incentivisation on ART initiations, trends in number of ART initiations in the following facilities will be compared, and difference-in-difference estimates will be computed:

- Facilities with catchment areas where HIVST kits were distributed and CBDs were incentivised
- Facilities with catchment areas where HIVST kits were distributed and CBDs were *not* incentivised

To evaluate the overall effect of HIVST on ART initiations, trends in number of ART initiations in the following facilities will be compared, and difference-in-difference estimates will be computed:

- Facilities with catchment areas where HIVST was offered
- Facilities with catchment areas where HIVST was not offered

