- III. Refining procedures for facilitating and documenting linkage to prevention and care services after self-testing.

A detailed process evaluation will be conducted throughout the program implementation period.

Quasi experimental methods will be used to evaluate the effect of incentives for CBDs on ART initiations in each study district, and the overall effect of HIVST kit distribution on ART initiations.

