## 4.2.2 Randomisation

Thirty-eight outreach communities in the seven study districts will be randomised in a 1:1ratio to receive incentives for CBDs or no incentives. Randomisation will be performed by the study statistician. Restricted randomisation will be used to minimise imbalance in key factors between arms (district, HIV prevalence and proximity to a health facility). A public randomisation ceremony will be held to select the final allocation from a randomly-generated list of acceptable allocations.

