## Evaluating the effect of HIVST and CBD incentivisation on ART initiations in the study districts

Using a standard data collection form (Appendix 3), data on monthly number of ART initiations will be abstracted from records of all health facilities in each study district for the following periods:

- Six months before distribution of HIVST test kits is started
- During period of HIVST kit distribution
- Three months after HIVST kit distribution has been completed

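### Difference-in-differences on facility ART initiations gives away some precision on the randomised incentive contrast, and the objectives name a different method for it

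*Protocol*

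**What the plan says.** Protocol section 4.2.2 makes the incentive a randomised factor: 38 "outreach communities in the seven study districts will be randomised in a 1:1ratio to receive incentives for CBDs or no incentives".

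Section 4.2.4, under the heading on ART initiations in the study districts, sets up the facility data: "data on monthly number of ART initiations will be abstracted from records of all health facilities in each study district". The periods run from "Six months before distribution of HIVST test kits is started", through distribution, to "Three months after HIVST kit distribution has been completed".

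Three places then describe the analysis of the incentive effect on these counts:

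- Section 2, Secondary Objectives, assigns it to time-series methods and reserves difference-in-differences for the overall effect of self-testing.
- Section 3 says: "Quasi experimental methods will be used to evaluate the effect of incentives for CBDs on ART initiations in each study district".
- Section 6, Analysis of health facility data, says: "To evaluate the effect of CBD incentivisation on ART initiations, trends in number of ART initiations in the following facilities will be compared". The groups are incentivised and non-incentivised facilities (the first being "Facilities with catchment areas where HIVST kits were distributed and CBDs were incentivised"). The same sentence goes on to name the estimator: trends "in the following facilities will be compared, and difference-in-difference estimates will be computed". The same method is given for facilities where self-testing was or was not offered.

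The protocol nowhere plans to adjust facility counts for their own baseline. The cluster-trial paragraph of section 6 mentions adjustment only for cluster HIV prevalence and other key characteristics.

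**The concern.** Section 6 uses one estimator for two comparisons that are identified differently. Self-testing offered against not offered is not randomised. There DiD does necessary work, because it removes fixed differences between areas. Incentive against no incentive is randomised, so that protection is not needed for validity.

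DiD is the post-period contrast minus exactly 1 times the baseline contrast. If facility counts are noisy, part of any baseline difference is chance, and subtracting all of it carries that noise into the estimate. An estimated slope subtracts only the share that predicts the later count.

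What is at stake is the width of the interval for a stated secondary objective. The number of clusters is fixed, so further precision has to come from the analysis. In addition, a reader cannot tell from the protocol which method is planned, because the objectives and section 6 disagree.

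**Working it through.** **The plan's own figures.** The protocol gives no power for ART initiations. Its only power table (section 6) is for linkage in the survey. With 19 clusters per arm, 200 respondents, k = 0.3 and an assumed two-sided 5% level:

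power = Φ( |p1 − p0| / √{[p1(1−p1)/200 + p0(1−p0)/200 + 0.3²(p1² + p0²)]/18} − 1.96 )

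| Intervention v control | Stated | Recomputed |
|---|---|---|
| 15% v 10% | 92% | 91.8% |
| 7.5% v 5% | 83% | 83.3% |
| 20% v 14% | 87% | 87.2% |

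The table is sound, and this point does not touch it.

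**Inputs for the ART analysis.** From the protocol: 38 randomised wards, 19 per arm; six pre-distribution months. Assumed, because the protocol does not state them: the pre–post correlation rho, equal pre and post variance σ², and one independent unit per ward.

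**Variance per unit.**
- DiD: 2σ²(1 − rho)
- Baseline-adjusted: σ²(1 − rho²)
- Ratio, adjusted to DiD: (1 − rho²)/[2(1 − rho)] = (1 + rho)/2

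With unequal variances the large-sample excess of DiD is (σ_pre − rho·σ_post)², which is never negative. Below rho = 0.5, DiD has a larger variance than ignoring the baseline: at rho = 0.3 it is 1.40σ² against 1.00σ².

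**Cost of estimating the slope.** With 38 units, multiply the adjusted variance by 1 + 1/(38 − 4) = 35/34. Break-even is where (1 + rho)/2 × 35/34 = 1, so rho = 68/35 − 1 = 0.943.

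**Power.** Start from an effect that DiD detects with 80% power (two-sided 5%, 36 df, non-centrality 2.879). Divide 2.879 by the square root of the variance ratio and use 35 df.

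| rho | (1+rho)/2 | × 35/34 | Non-centrality | Power, adjusted |
|---|---|---|---|---|
| 0.3 | 0.65 | 0.669 | 3.520 | 92.8% |
| 0.5 | 0.75 | 0.772 | 3.277 | 89.0% |
| 0.7 | 0.85 | 0.875 | 3.078 | 84.9% |
| 0.8 | 0.90 | 0.926 | 2.991 | 82.9% |
| 0.9 | 0.95 | 0.978 | 2.911 | 80.8% |
| 0.95 | 0.975 | 1.004 | 2.874 | 79.8% |

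A gain of about 5 points therefore needs rho of about 0.7 or less.

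**Check on counts.** Poisson counts were simulated for 38 units with 6 pre-months, 4 post-months (assumed) and a true log-rate effect of 0.2, with 6,000 runs per row. The analysis used log rates with 0.5 added to each count.

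| Between-facility log-SD | Facility-by-period log-SD | Initiations a month | rho | SE, DiD | SE, adjusted | Variance ratio |
|---|---|---|---|---|---|---|
| 0.3 | 0.3 | 5 | 0.39 | 0.167 | 0.144 | 0.75 |
| 0.5 | 0.3 | 5 | 0.63 | 0.170 | 0.158 | 0.86 |
| 0.5 | 0.2 | 10 | 0.78 | 0.116 | 0.111 | 0.91 |
| 0.8 | 0.2 | 10 | 0.90 | 0.122 | 0.120 | 0.98 |
| 1.0 | 0.15 | 20 | 0.96 | 0.090 | 0.090 | 1.01 |

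Bias was below 0.005 for both estimators in every row. The gain shrinks as facilities differ more in size, because rho then rises.

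**The case against.** **Nothing here is invalid.** This is right. DiD is unbiased under randomisation. A reader might infer that a quasi-experimental label on a randomised contrast means a biased estimate or an inflated type I error. Neither the documents nor the simulations support that.

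**The gain may be negligible.** This also stands. Section 4.2.4 takes in every health facility in each district, and their sizes may vary widely. In further simulations of a 35% rise (19 facilities per arm, facility-by-period log-SD 0.2, all assumed), the power gain was 7–10 points with a between-facility log-SD of 0.3. It was only 0.4–2.1 points with a log-SD of 0.8–1.0. It would be too strong to say that adjustment is always more precise.

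**The unit is uncertain.** Section 6 defines groups by facility catchment, and neither the number of facilities nor their mapping to wards is given. The 38 units above are an assumption.

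**Model form can wait for the analysis plan.** This stands only in part. Comparing trends in monthly counts leaves room for more than a two-period change score. But section 6 does name the estimator, and the objectives name another, so the protocol has fixed something and fixed it inconsistently.

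**ART initiation is already compared by arm.** The survey includes the proportion of HIV positives initiated on ART as a secondary outcome, analysed by intention to treat. That limits the consequence. The facility analysis nevertheless answers its own stated objective.

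**Conclusion.** The point holds as a modest matter of precision on a secondary objective, together with an inconsistency between the Secondary Objectives and section 6. It is not a matter of bias, and the primary outcome and its power are unaffected.

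The size depends on rho, which the protocol does not give. Under the 38-unit, equal-variance assumptions, power rises from 80% to between 81% (rho 0.9) and 93% (rho 0.3). It does not change near rho 0.94, and above that the variance is 1–2% larger at most in the range tried. A material gain at low or moderate rho is thus set against a trivial loss at very high rho. Because adjustment estimates the slope, rho need not be known in advance.

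The criticism does not extend to the comparison of areas with and without self-testing, where DiD is a reasonable choice.

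**What to change.** In section 6, Analysis of health facility data, and to match in the Secondary Objectives and section 3, describe incentive against no incentive as the randomised comparison. Specify:

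- a Poisson or negative binomial model of post-distribution ART initiations on arm;
- the facility's six-month pre-distribution rate as a covariate, in a form that handles zero counts, such as the log of the count plus 0.5;
- calendar time, since the timeline spreads distribution over 12 months;
- the restricted-randomisation factors (district, HIV prevalence, proximity to a health facility);
- inference at the level of the randomised ward.

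Keep DiD as the main method for self-testing offered against not offered, and as a sensitivity analysis for the incentive contrast.

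The cost is a change of wording. The baseline counts are already to be abstracted. Compared with DiD on the same other covariates, the model estimates one more parameter, with a negligible loss of precision if rho is very high. The design factors use further degrees of freedom under either method. With seven districts and 38 wards, the analysis plan should say how district enters.
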